5.2. Effectiveness Populations

5.2.1. Primary Effectiveness Population

The Primary-Effectiveness Population is defined as subsets of the migalastat-treated group, the untreated group, and ERT-treated group as comparators.

Patients who enter the study as untreated but switch to a treatment (migalastat or ERT) within 3 months from enrollment will be considered in analysis as initially belonging to a treatment group they switched to. Depending on an analysis as further discussed the group assignment might change in the case of a treatment switch.

All data collected will be utilized to establish the Primary Effectiveness Population for the analysis. Patients need to have a documented amenable variant to be included in the Primary Effectiveness Population and must meet criteria for receiving treatment for migalastat.

All patients from the Danish National Fabry Centre will be included, estimating the inclusion of 115 individuals (sex ratio [female:male] – 2:1). Pre-specified subgroups include: non-amenable/ amenable to migalastat, males/females.

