3.2. Secondary Effectiveness Analysis

Secondary endpoints listed below will be assessed by evaluating migalastat-treated and untreated patients and/or migalastat-treated and ERT-treated patients:

- The prevalence of FACEs from each baseline (diagnosis, and start of treatment) in migalastat-treated, ERT-treated patients and untreated patients

- The incidence of FACEs from each baseline (diagnosis, and start of treatment in migalastat-treated, ERT-treated patients and untreated patients
- Time to the first cardiac, cerebrovascular, and renal clinical event separately by each specific category (including death in these categories) from baseline (diagnosis and start of each treatment) using Cox proportional hazards model and descriptive statistics.
- Incidence of cardiac, cerebrovascular, and renal clinical events separately by each specific category (including death in these categories)
- Occurrence of cardiac, cerebrovascular, and renal clinical events separately by each specific category (including death in these categories)
- Annualized rate of change in eGFR based on the Chronic Kidney Disease Epidemiology Collaboration equation (eGFR CKD-EPI) over time in migalastat-treated, ERT, and untreated patients . Analysis will also be performed by eGFR category at baseline if the counts are sufficient.
- The prevalence and incidence of a clinically significant change in mGFR and/or eGFR (according to KDIGO guidelines rapid progression is defined as a sustained decline in eGFR of more than 5 ml/min/1.73 m²/yr) from each baseline (diagnosis, and start of treatment) in migalastat-treated, ERT-treated patients and untreated patients.
- The prevalence and incidence of micro (> 30 mg/g creatinine) or macroalbuminuria (> 300) by urinary albumin/creatinine ratio (ACR) or urinary 24 h protein excretion from each baseline (diagnosis, and start of treatment) in migalastat-treated, ERT-treated patients and untreated patients.

The analysis for the primary effectiveness endpoint will be performed at the 2-sided significance level of 0.05 to compare migalastat-treated and untreated patients. All other comparisons will also be done at the 2-sided significance level of 0.05 with no adjustment for multiple comparisons.

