5.2.2. Secondary Effectiveness Population

Secondary Effectiveness Population will include all patients regardless of the variant.

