13. ANALYSIS OF EFFECTIVENESS

13.1. Primary Endpoint

The comparison of interest is between migalastat-treated and untreated patients in the Primary and Secondary Effectiveness Populations. The analysis for the primary effectiveness endpoint will be performed at the 2-sided significance level of 0.05. This analysis will be performed when enough data are available.

Clinical effectiveness will be based on FACEs of cardiac, cerebrovascular, and renal events, and deaths due to FACEs. A composite event is defined as the occurrence of either cardiac, cerebrovascular, or renal clinical event, and death due to FACEs.

Subject matter experts will adjudicate all reports of FACEs. For all summary analyses, the adjudicated decisions will be used if they differ from the initial report. Both original and adjudicated decisions will be reported in listings. Only adjudicated decisions will be used for analyses.

Analyses will be performed in the Primary and Secondary Effectiveness Population.

The analyses described further in Section **Error! Reference source not found.** through Section **Error! Reference source not found.** will be performed for the endpoint of all FACEs combined and separately for all specific FACEs categories listed above (including deaths in these categories) as supportive analyses. A separate analysis of all deaths due to FACEs will also be conducted.

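### SAP 13.1 tests the primary endpoint at 0.05 in two populations without saying which one decides, and a misplaced whole-cohort paragraph in 5.2.1 conflicts with the amenable-variant rule

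*SAP*

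**What the plan says.** SAP 5.2.1 gives two criteria for the Primary Effectiveness Population. The first is genetic: "Patients need to have a documented amenable variant to be included in the Primary Effectiveness Population". The second is that the patient meets the criteria for receiving migalastat. The next paragraph under the same heading reads "All patients from the Danish National Fabry Centre will be included, estimating the inclusion of 115 individuals", gives the sex ratio, and continues: "Pre-specified subgroups include: non-amenable/ amenable to migalastat, males/females".

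SAP 5.2.2 defines the other set: "Secondary Effectiveness Population will include all patients regardless of the variant".

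SAP 13.1 uses both sets for the primary endpoint: "The comparison of interest is between migalastat-treated and untreated patients in the Primary and Secondary Effectiveness Populations". It then sets the level: "The analysis for the primary effectiveness endpoint will be performed at the 2-sided significance level of 0.05". Further down it repeats: "Analyses will be performed in the Primary and Secondary Effectiveness Population".

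SAP 3.2 sets the same level for migalastat versus untreated without naming a population, and adds: "All other comparisons will also be done at the 2-sided significance level of 0.05 with no adjustment for multiple comparisons".

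The Cox model in SAP 13.1.1 adjusts for sex, age, eGFR, LVMi, previous clinical events and length of Fabry treatment. It names no population.

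**The concern.** A primary test needs one analysis set. Here the same comparison, endpoint and significance level apply to two sets, and the documents do not say what follows if the results disagree. In a retrospective study, that leaves the headline result open to choice after the data are seen.

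The two sets also answer different questions. The protocol's background section describes migalastat as an option for patients with amenable mutations. In the amenable set, the untreated comparators carry variants for which the drug was an option. In the all-variant set, the untreated arm also holds patients who could not have been given it. Any prognostic difference between amenable and non-amenable variants then enters the hazard ratio, and no listed covariate removes it.

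The paragraph on 115 individuals adds a practical problem. A programmer building the primary dataset from 5.2.1 finds a rule that excludes non-amenable patients, followed by a statement that everyone is included and a subgroup that the rule leaves empty.

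**Working it through.** **Is a deciding population named anywhere?**

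- SAP 13.1 names both populations jointly, twice, with no order and no alpha split.
- SAP 3.2 gives the level but no population.
- SAP 13.1.1 gives the model but no population.
- The protocol's section on primary endpoint analysis names no population.

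So the hierarchy is not stated.

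**How should 5.2.1 be read?** If the 115 paragraph defined the Primary population, it would coincide with the all-variant set of 5.2.2, and a separate Secondary population would be redundant. The paragraph nearly repeats the protocol's study-population text, including the sex ratio and the subgroup list. The only reading that fits 5.2.1 and 5.2.2 together is an amenable-only Primary population with a cohort description in the wrong place.

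**Does the model separate genotype from treatment?** The covariates in 13.1.1 include no variant, amenability or phenotype term. Section 12 lists a classic versus non-classic phenotype subgroup but none for amenability.

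**Error rate if either result may count.** The SAP has no figure to reproduce: section 4 says the sample size was not determined statistically, and the documents give no amenable share or event count. The event shares below are therefore assumptions, shown as a range.

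1. Upper limit, if the two tests were independent: 1 − 0.95² = 0.0975.
2. The tests are not independent. The migalastat arm should be largely common to both sets, and mainly the untreated arm changes. Let d_m be the migalastat events, d_a the untreated events in amenable patients, and d_u the untreated events in all patients. The variance of the log hazard ratio is about 1/d_m + 1/d_a in the amenable set and 1/d_m + 1/d_u in the all-variant set. If neither treatment nor genotype has an effect, the correlation of the two test statistics is ρ = √[(1/d_m + 1/d_u) / (1/d_m + 1/d_a)].
3. Let m be the migalastat share of primary-population events and q the amenable share of untreated events. Then d_m = m, d_a = 1 − m and d_u = (1 − m)/q, up to a common factor that cancels.
4. Example, m = 0.35 and q = 0.5: d_a = 0.65 and d_u = 1.30, so ρ = √[(2.857 + 0.769)/(2.857 + 1.538)] = √0.825 = 0.908.
5. P(at least one |z| > 1.96) from the bivariate normal with that correlation:

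| m | q | ρ | Chance of at least one false positive |
|---|---|---|---|
| 0.20 | 0.25 | 0.922 | 6.8% |
| 0.20 | 0.50 | 0.949 | 6.5% |
| 0.20 | 0.75 | 0.975 | 6.0% |
| 0.35 | 0.25 | 0.859 | 7.4% |
| 0.35 | 0.50 | 0.908 | 7.0% |
| 0.35 | 0.75 | 0.955 | 6.4% |
| 0.50 | 0.25 | 0.791 | 7.9% |
| 0.50 | 0.50 | 0.866 | 7.3% |
| 0.50 | 0.75 | 0.935 | 6.7% |

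The range is 6.0% to 7.9%, against a nominal 5%. With one deciding population it returns to 5%.

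**The case against.** The strongest reply is that the SAP calls one set Primary and the other Secondary, so the order is plain and only a sentence is missing. The labels do suggest that the amenable set was meant to lead. But 13.1 is where the test is specified, and it names both sets as the comparison of interest at the same level. The labels make the remedy easy; they do not supply the rule.

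A second reply is that a family-wise error rate is a weak measure of harm here. The study has no statistical sample size, leaves its other comparisons openly unadjusted, and puts its main interest in describing effectiveness under migalastat. That largely stands: the inflation is moderate, and the free choice of headline result matters more.

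A reader might infer that the Primary population is truly defined in two ways, and that this and the double test together leave no primary result. The documents do not support that. Section 5.2.1 has one inclusion rule, and 5.2.2 makes sense only if that rule governs. The two complaints also cannot both produce the inflation: if the 115 paragraph governed, the two sets would coincide and there would be a single test.

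A reader might also put the false-positive risk at 9% or more. Nesting alone, with the amenable set carrying 20% of the information, gives 9.2%, but that ignores the shared migalastat arm. Within the shared-arm formula, a correlation near 0.63 and a risk of 8.6% require, for example, the migalastat arm to hold 80% of primary-population events with q = 0.25. Nothing in the documents points there.

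**Conclusion.** The point holds as an unstated hierarchy in SAP 13.1, made worse by a misplaced paragraph in 5.2.1. Followed as written, the plan yields two primary results for one endpoint, and one of them uses untreated comparators who could not have received migalastat, with no covariate for it.

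The chance of at least one false positive is about 6-8%. That rests on a migalastat arm shared by both sets, the assumed event shares (m of 20-50%, q of 25-75%), and no covariate adjustment in the approximation. Any genotype difference comes on top. The documents give no basis for its size or direction, so a claim that the all-variant result would favour or disfavour migalastat would go too far. No power figure can be given either.

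This should be corrected before analysis. It concerns which result counts as primary, and SAP wording repairs it fully.

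**What to change.** - **SAP 13.1:** state that the primary test at two-sided 0.05 is migalastat versus untreated in the Primary Effectiveness Population, as defined by both criteria in 5.2.1 (documented amenable variant, and meeting the criteria for receiving migalastat). Label the Secondary Effectiveness Population result supportive, reported as an estimate with confidence interval and no claim.
- **SAP 5.2.1:** move the 115 paragraph to the study description in section 2 or section 4. Simple deletion would lose the amenability subgroup, which the protocol pre-specifies, section 2 mentions only conditionally on numbers, and section 12 does not list.
- **SAP 12:** add amenable versus non-amenable as a subgroup of the Secondary Effectiveness Population, where both groups exist.

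If the sponsor wants both populations to carry a claim, the SAP needs a fixed testing order or an alpha share instead. Bonferroni gives 0.05/2 = 0.025 per test.

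The cost is SAP wording only, with no new data and no change in conduct. What is given up is the option of presenting the all-variant result as the primary finding.

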5.2.2. Secondary Effectiveness Population

Secondary Effectiveness Population will include all patients regardless of the variant.

6. HANDLING OF DROPOUTS AND MISSING VALUES

6.1. Imputation of Dates

SAEs and FACEs

If onset date is completely missing, then the onset date is set to the date of enrollment unless end date is before the date of enrollment, in which case the onset date is set to 28 days prior to end date.

If (year is present and month and day are missing) or (year and day are present and month is missing):

- If year = year of enrollment, then set month and day to month and day of enrollment unless end date is before the date of enrollment, in which case the onset date is set to 28 days prior to end date.
- If year < year of enrollment, then set month and day to 31 December.
- If year > year of enrollment, then the following applies:
 - If year = year of first treatment switch, then set month and day to month and day of first treatment switch unless end date is before the date of treatment switch, in which case the onset date is set to 28 days prior to end date.
 - If there is no treatment switch, then set month and day to 1 January.

If month and year are present and day is missing:

- If year = year of enrollment and if month = month of enrollment, then set day to day of enrollment date unless end date is before the date of enrollment, in which case the onset date is set to 28 days prior to end date.
- If month < month of enrollment, then set day to last day of the month.
- If month > month of enrollment, then the following applies:
 - If year = year of first treatment switch and if month = month of first treatment switch, then set the day to the day of treatment switch unless end date is before the date of treatment switch, in which case the onset date is set to 28 days prior to end date.
 - If there is no treatment switch, then set day to first day of the month.

For all other cases, set onset date to the date of enrollment unless end date is before the date of enrollment, in which case the onset date is set to 28 days prior to end date.

End date will not be imputed.

Start and End of Therapy Prior to Study Enrollment

The following dates are essential for analysis: the end date of Fabry disease therapy prior to enrollment and the start date of ongoing Fabry therapy for the migalastat-treated patients and for the ERT-treated patients. These dates will be used to determine treatment duration prior to enrollment.

Prior to imputation of dates, the percentage of patients with completely missing start of therapy date, and separately with missing month will be calculated and presented in a table overall and by treatment group at enrollment.

Similarly, the percentage of patients with completely missing end of therapy date, and separately with missing month will be calculated and presented in a table overall and by treatment group at enrollment.

At least the year needs to be present to determine if the patients are eligible for inclusion in the Primary and Secondary Effectiveness Populations.

The following rules apply to the start date:

- If year is present and month and day are missing: set month and day to 1 July.
- If year and day are present and month is missing: set month to July.
- If year and month are present and day is missing: set day to the 15th of the month.

The following rules apply to the end date:

- If the end date is completely missing and the patient did not switch therapy, then the end date is imputed as the discontinuation date.
- If the end date is completely missing and the patient switched therapy, then the end date is imputed as the therapy switch date.
- If year is present and different from the year of the start date, and month and day are missing: set month and day to 1 July.
- If year is present and the same as the year of the start date, and month and day are missing: set month and day to 31 December.
- If year and day are present and month is missing: set month to July.
- If year and month are present and day is missing: set day to the 15th of the month.

Any partial dates will be displayed in data listings without and with imputation of missing days and/or months.

Treatment Switch

Prior to imputation of dates, the percentage of patients with completely missing switch of therapy date, and separately, the percentage of patients with missing month will be calculated and presented in a single table overall, and by treatment group at enrollment. Patients can change therapy more than once during the 20-year period. The percentages of patients with any completely missing switch of therapy dates or any missing therapy switch month will be presented. Additionally, a table with percentages of missing switch dates by group a patient switched to (migalastat-treated, ERT, untreated) will be presented.

The following rules apply to start date of new or switched therapy:

- If start date is completely missing: start date will be imputed as 30 days past enrollment date.

- If (year is present and month and day are missing) or (year and day are present and month is missing): set month and day to the date of the first closest visit, unless another switch occurred before it. In such a case, set the start date to the date of the previous visit.
- If year and month are present and day is missing: set day to the first day of the month unless during that month there was a visit, in which case the day will be set to the day of that visit.

The following rules apply to end date of new or switched therapy:

- If end date is completely missing: end date will not be imputed unless there is another treatment switch. In that case, the end date is imputed as a day before that next treatment switch.
- If (year is present and month and day are missing) or (year and day are present and month is missing): set month and day to the date of the last visit in that year, unless another switch occurred. In such a case, set the end date to a day before that next treatment switch.
- If year and month are present and day is missing: set day to the date of the last day of the month.

Any partial dates will be displayed in data listings without and with imputation of missing days and/or months.

Concomitant Medications

The following rules apply to start date:

- If start date is completely missing: start date will not be imputed.
- If (year is present and month and day are missing) or (year and day are present and month is missing): set month and day to 1 January.
- If year and month are present and day is missing: set day to first day of the month.

The following rules apply to end date:

- If end date is completely missing: end date will not be imputed.
- If (year is present and month and day are missing) or (year and day are present and month is missing): set month and day to 31 December.
- If year and month are present and day is missing: set day to last day of the month.

Any partial dates will be displayed in data listings without imputation of missing days and/or months (eg, MAR2011, 2009). No other imputation of missing data will be performed.

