### *Registration of treatment*

All patients included in the trial are considered treatment naïve at inclusion in the observational period (01.01.2001). Registration of initiation, change or cessation of treatment will follow the following structure:

Date (Date)	Drug (Name)	Action* (Categorical)	Dose (Integer)	Dose interval (Comment)	Comment (Comment)
----------------	----------------	--------------------------	-------------------	----------------------------	----------------------

\*Action is restricted to four levels: initiation, increase, decrease, cessation.

Cardiac events		
Date of event	Cardiac event	Yes/No
	Myocardial infarction	Yes No
	Unstable angina pectoris	Yes

		No
	PCI / CABG	Yes No
	Heart Failure	Yes No
	Arrhythmia (New onset of symptomatic arrhythmia requiring anti-arrhythmic Medication)	Yes No
	Heart procedure (pacemaker/ICD/valve surgery)	Yes No

Renal events		
Date of event	Renal event	Yes/No
	Doubling of s-creatinine	Yes No
	ESKD	Yes No

Cerebrovascular events		
Date of event	Cerebrovascular event	Yes/No
	Stroke	Yes No
	TIA	Yes No

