2. OVERVIEW OF STUDY DESIGN

This is a retrospective study of prospectively collected patient data with the use of secondary patient data from both paper and electronic patient files. All patients are treatment naïve at time of diagnosis. Both migalastat and ERT will be studied retrospectively. Also untreated patients will be studied by assessment of relevant clinical and laboratory variables. The analysis will originate at the time of diagnosis.

The patients have been followed for more than 20 years from 2001 until December 2023. All identified patients with Fabry disease, whether receiving specific Fabry medication or not, have been offered annual or biannual thorough workups including examinations of Fabry associated organ function and symptoms. The study will be carried out at the Danish National Fabry Centre, Department of Endocrinology, Copenhagen University Hospital.

All patients from the Danish National Fabry Centre will be included. Subgrouping is aimed at depending on available numbers: non-amenable, amenable, classic, non-classic, males, females, treated including type of treatment or untreated.

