11. DEFINITION OF STUDY TIME POINTS

11.1. Definition of Diagnosis Date

Enrollment is the date on which the patient was diagnosed with the Fabry disease. For analysis of assessments which were not collected on the diagnosis date, the assessment closest to the diagnosis date will be utilized. If there are 2 assessments that are equidistant from the diagnosis date, then the assessment prior to diagnosis will be utilized.

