15.1. Approach to Safety Analyses

As this is an observational study, patients may switch or stop therapies. In the Safety Population, analysis will present results based on the actual exposure, ie, treatment group at the time of the event (migalastat, ERT, or untreated). As patients can stop or switch therapy while enrolled in the study, they might be counted more than once in the analysis.

Serious adverse events will be analysed as described in Section 13 for the composite FACES.

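### Undated SAEs and FACEs default to the diagnosis date, so in the exposure-based rates on-treatment events can be counted in untreated time

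*SAP*

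**What the plan says.** For SAEs and FACEs, SAP 6.1 gives this rule: "If onset date is completely missing, then the onset date is set to the date of enrollment". The one exception reads "unless end date is before the date of enrollment, in which case the onset date is set to 28 days prior to end date". An end date after enrollment plays no part.

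Partial dates have their own branches. An event in the year of the first treatment switch goes to the switch date (subject to an end-date check), and an event in a patient who never switched goes to the start of the known year or month. Whatever is left falls to a closing line: "For all other cases, set onset date to the date of enrollment".

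Three other passages fix what this means:

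- SAP 11.1: "Enrollment is the date on which the patient was diagnosed with the Fabry disease".
- SAP 2: "All patients are treatment naïve at time of diagnosis". The protocol agrees under Registration of treatment: "All patients included in the trial are considered treatment naïve at inclusion in the observational period".
- SAP 15.1, for safety: "analysis will present results based on the actual exposure, ie, treatment group at the time of the event". SAP 15.3 bases SAE incidence on that exposure. SAP 13.3 counts FACEs between diagnosis and therapy start as untreated, and counts FACEs on therapy as treated.

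SAP 5.1 and 5.2.1 add a qualification: a patient who starts migalastat or ERT within 3 months of enrollment is treated in the analysis as initially belonging to that treatment group.

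**The concern.** Taken together, these rules give an undated event a date on which the patient was on no Fabry therapy. If the event really happened on migalastat or ERT, it is removed from the treated numerator and added to the untreated one, while person-time stays where it was. This holds even when the record contains an end date in the treated period or rates the event as definitely caused by the drug. For safety, the result is a treated SAE rate that is too low and an untreated comparator rate that is too high.

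The data come from paper and electronic files reaching back to 2001, and SAP 6.2 itself anticipates missing or partial SAE dates. SAP 6.1 plans tables of missing therapy dates, but none of missing SAE or FACE onset dates. No sensitivity analysis of the rule is planned. With about 115 patients, a few misplaced events could be visible in the rates.

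**Working it through.** The SAP gives no event rate, power or missing-date figure to reproduce. The check has three parts.

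**1. Trace of the rule.** Take an illustrative patient diagnosed on 10 March 2005 whose first therapy starts on 1 June 2017. Starting therapy counts as the first switch, as SAP 5.1 uses the word.

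| Recorded onset | Recorded end | Branch of SAP 6.1 | Imputed onset | Counted as |
|---|---|---|---|---|
| none | none | fully missing | 10 March 2005 | untreated |
| none | 1 May 2019 | fully missing; exception not met | 10 March 2005 | untreated |
| 2019 only | none | fallback | 10 March 2005 | untreated |
| 2010 only | none | fallback | 10 March 2005 | untreated (right state, too early) |
| 2017 only | none | year of first switch | 1 June 2017 | treated |

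Row 2 implies an event lasting just over 14 years. The SAP's own 28-day convention, if it were extended to later end dates, would give 3 April 2019, which is on therapy. Row 3 discards a known year that lies wholly after therapy start. Row 5 works in the opposite direction: an event from early 2017, before therapy, would be charged to therapy.

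**2. Effect on an exposure-based rate.** Let both states have the same true event rate λ, let k be treated person-time divided by untreated person-time, and let m be the share of on-treatment events that have no usable onset date. Undated events that truly occurred while untreated stay untreated, so they do not alter the count.

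- Treated rate as analysed: λ(1 − m)
- Untreated rate as analysed: λ(1 + mk)
- Apparent rate ratio: (1 − m)/(1 + mk), where the truth is 1.00

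Both m and k are assumptions, because the documents give neither.

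| m | k = 0.5 | k = 1 | k = 2 |
|---|---|---|---|
| 2% | 0.97 | 0.96 | 0.94 |
| 5% | 0.93 | 0.90 | 0.86 |
| 10% | 0.86 | 0.82 | 0.75 |
| 20% | 0.73 | 0.67 | 0.57 |

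Example: with λ = 20 per 1000 person-years, k = 1 and m = 10%, the treated rate reads 20 × 0.90 = 18 and the untreated rate 20 × 1.10 = 22. The ratio is 18/22 = 0.82.

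The formula counts events, which matches the analysis-methods line of SAP 13.3 and the recurrent-event summaries in SAP 7.3. SAP 15.3, and another line of 13.3, count patients with at least one event. There the formula is only a guide, because a patient with a second, dated event on the same therapy is still counted.

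**3. Time-to-event comparisons.** SAP 11.2 starts the clock at diagnosis for migalastat versus untreated. SAP 3.1 starts it at treatment start for treated patients. For an undated FACE in a patient of the migalastat cohort:

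- Under 11.2 it could be a day-1 event charged to migalastat, or be excluded as not on therapy.
- Under 3.1 it falls before time zero and becomes prior history.

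In migalastat versus ERT both groups start at treatment start, so both lose their undated events.

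**The case against.** Several points against the concern have force.

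- **The primary result.** A reader might infer that the rule tilts the primary Cox comparison towards migalastat. The documents do not support that: depending on whether SAP 3.1 or 11.2 governs, the same event can count against migalastat, drop out, or become a covariate. Nor does any direction follow for migalastat versus ERT.
- **Not every patient, and not every branch.** Patients who start therapy within 3 months carry the treated label from the outset, so their undated events may be charged to treatment. SAP 6.1 and SAP 10 also refer to Fabry therapy before enrollment, which sits badly with all patients being treatment naïve at diagnosis. The switch-year branch can move untreated events onto therapy. It is therefore too strong to say that Section 6.1 as a whole errs one way; its net effect has not been assessed.
- **Frequency.** The existence of a rule does not show that many events are undated. The protocol's form has a date field for each FACE, and its Study workflow section says data points are registered by date. At 2% undated and equal person-time the ratio is 0.96. If undated events are mostly early and pre-treatment, untreated is the right label and the distortion is small.
- **Recorded attribution.** SAP 15.2 collects causality against current treatment, including a category for untreated at the time of the event. One could argue that this field, and not the imputed date, would decide. No passage says so, and SAP 15.5 calculates exposure from imputed dates.

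These points limit scope and size. They do not remove the misattribution, because the only exception moves an event still earlier and never returns one to a treated period.

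**Conclusion.** The concern stands for SAE incidence and FACE incidence by actual exposure. A fully undated event that truly occurred on migalastat or ERT, and some events with a known on-treatment year, are counted as untreated, outside the group covered by the 3-month rule. For those events the shift lowers treated rates relative to untreated rates.

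The size is illustrative: about 0.96, 0.90 and 0.82 instead of 1.00 when 2%, 5% and 10% of on-treatment events are undated. This assumes equal true rates, equal person-time and rates that count events. The real share is unknown and may be small.

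For the primary Cox comparison, what can be said is that the rule places events at or before time zero. Its direction stays open until SAP 3.1 and 11.2 are reconciled. A claim that it favours migalastat there would go beyond the documents.

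**What to change.** Amend SAP 6.1 for SAEs and FACEs with a missing onset:

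1. Use the recorded end date, any known year, and the recorded causality or treatment-at-event field to assign the event to the treatment then in force. Do not default to enrollment, in the first rule or in the fallback, when these show that the event occurred on treatment. An end date alone bounds onset only from above, so the SAP should state which item prevails when they disagree.
2. Report the number of events that still cannot be placed, by patient treatment history, under a label such as *treatment unknown*.
3. Run the rate and time-to-event analyses twice, with those events assigned first to untreated and then to treated time. This keeps them in the analysis and shows whether the choice matters.
4. Reconcile SAP 3.1 and 11.2 on the start of the clock, so that the effect on the primary model can be stated.

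The cost is SAP wording, a little more programming and one extra run of the affected tables. The downside is that a few events will be shown with unknown attribution.
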